7.1.2. Liver Injury

A participant who meets any of the following will be withdrawn from the study intervention.[16]

- ALT or AST $> 8 \times ULN$;
- ALT or AST >5 × ULN for more than 2 weeks;
- ALT or AST >3 × ULN and (T bili >2 × ULN or INR >1.5);
- ALT or AST >3 × ULN with the appearance of fatigue, nausea, vomiting, right upper quadrant pain or tenderness, fever, rash, and/or eosinophilia (>5%).

See Section 10.6 for Potential Cases of Drug Induced Liver Injury.

7.1.3. ECG Changes

A participant who meets either bulleted criterion based on the average of triplicate ECG readings will be withdrawn from the study intervention.

- QTcF >500 ms.
- Change from baseline: QTcF >60 ms and QTcF >450 ms.

If a clinically significant finding is identified (including, but not limited to, changes from baseline in QTcF after enrollment), the investigator or qualified designee will determine if the participant can continue in the study and if any change in participant management is needed. This review of the ECG printed at the time of collection must be documented. Any new clinically relevant finding should be reported as an AE.

7.1.4. COVID-19

If a participant has COVID-19 during the study, this should be reported as an AE or SAE (as appropriate) and appropriate medical intervention provided. Study treatment should continue unless the investigator/treating physician is concerned about the safety of the participant, in which case temporary or permanent discontinuation may be required.

It is recommended that the investigator discuss temporary or permanent discontinuation of study intervention with the study medical monitor.

7.2. Participant Discontinuation/Withdrawal From the Study

A participant may withdraw from the study at any time at their own request. Reasons for discontinuation from the study include the following:

- Refused further study procedure;
- Lost to follow-up;
- Death;
- Study terminated by sponsor;
- Discretion of the investigator or sponsor for safety or behavioral reasons, or the
 inability of the participant to comply with the protocol required schedule of study
 visits or procedures.

At the time of discontinuing from the study, if possible, an early discontinuation visit should be conducted. See the SoA for assessments to be collected at the time of study discontinuation and follow-up and for any further evaluations that need to be completed.

The early discontinuation visit applies only to participants who are enrolled/randomized and then are prematurely withdrawn from the study. Participants should be questioned regarding their reason for withdrawal.

The participant will be permanently discontinued from the study intervention and the study at that time.

If a participant withdraws from the study, they may request destruction of any remaining samples taken and not tested, and the investigator must document any such requests in the site study records and notify the sponsor accordingly.

If the participant withdraws from the study and also withdraws consent (see Section 7.2.1 for disclosure of future information, no further evaluations will be performed and no additional data will be collected. The sponsor may retain and continue to use any data collected before such withdrawal of consent.

7.2.1. Withdrawal of Consent

Participants who request to discontinue receipt of study intervention will remain in the study and must continue to be followed for protocol-specified follow-up procedures. The only exception to this is when a participant specifically withdraws consent for any further contact with them or persons previously authorized by the participant to provide this information. Participants should notify the investigator in writing of the decision to withdraw consent from future follow-up, whenever possible. The withdrawal of consent should be explained in detail in the medical records by the investigator, as to whether the withdrawal is only from further receipt of study intervention or also from study procedures and/or posttreatment study follow-up, and entered on the appropriate CRF page. In the event that vital status (whether

the participant is alive or dead) is being measured, publicly available information should be used to determine vital status only as appropriately directed in accordance with local law.

7.3. Lost to Follow-Up

A participant will be considered lost to follow-up- if the participant repeatedly fails to return for scheduled visits and is unable to be contacted by the study site.

The following actions must be taken if a participant fails to return to the clinic for a required study visit:

- The site must attempt to contact the participant and reschedule the missed visit as soon as possible. Counsel the participant on the importance of maintaining the assigned visit schedule and ascertain whether the participant wishes to and/or should continue in the study;
- Before a participant is deemed lost to follow-up, the investigator or designee must make every effort to regain contact with the participant (where possible, 3 telephone calls and, if necessary, a certified letter to the participant's last known mailing address or local equivalent methods). These contact attempts should be documented in the participant's medical record;
- Should the participant continue to be unreachable, the participant will be considered to have withdrawn from the study.

8. STUDY ASSESSMENTS AND PROCEDURES

8.1. Administrative and Baseline Procedures

The investigator (or an appropriate delegate at the investigator site) must obtain a signed and dated ICD before performing any study-specific procedures.

Study procedures and their timing are summarized in the SoA. Protocol waivers or exemptions are not allowed.

Adherence to the study design requirements, including those specified in the SoA, is essential and required for study conduct.

All screening evaluations must be completed and reviewed to confirm that potential participants meet all eligibility criteria. The investigator will maintain a screening log to record details of all participants screened and to confirm eligibility or record reasons for screening failure, as applicable.

Participants will be screened within 28 days prior to administration of the study intervention to confirm that they meet the study population criteria for the study. If the time between screening and dosing exceeds 28 days as a result of unexpected delays (eg, delayed drug shipment), then participants do not require rescreening if the laboratory results obtained prior to first dose administration meet eligibility criteria.

A participant who qualified for this protocol but did not enroll from an earlier cohort/group may be used in a subsequent cohort/group without rescreening, provided laboratory results obtained prior to the first dose administration meet eligibility criteria for this study. In addition, other clinical assessments or specimen collections, eg, retained research samples, may not need to be repeated, as appropriate.

Every effort should be made to ensure that protocol-required tests and procedures are completed as described. However, it is anticipated that from time to time there may be circumstances outside the control of the investigator that make it unfeasible to perform the test. In these cases, the investigator must take all steps necessary to ensure the safety and well-being of the participant. When a protocol-required test cannot be performed, the investigator will document the reason for the missed test and any corrective and preventive actions that they have taken to ensure that required processes are adhered to as soon as possible. The study team must be informed of these incidents in a timely manner.

Any safety, laboratory or analyte results that have been collected for the purposes of this study and could unblind the study will not be reported to investigative sites or other blinded personnel until the study has been unblinded.

If done around the time of a blood draw, ECGs and vital sign assessments (BP and pulse rate) should be collected before the blood draw.

If an IV catheter is utilized for blood sample collections, ECGs and vital sign assessments (pulse rate and BP) should be collected prior to the insertion of the catheter.

For samples being collected and shipped, detailed collection, processing, storage, and shipment instructions and contact information will be provided to the investigator site prior to initiation of the study.

The total blood sampling volume for individual participants in Cohorts 1, 2 and 3 of this study are approximately 545, 440 and 340 mL, respectively. The actual collection times of blood sampling may change. Additional blood samples may be taken for safety assessments at times specified by Pfizer, provided the total volume taken during the study does not exceed 550 mL during any period of 56 consecutive days.

To prepare for study participation, participants will be instructed on the information in the Lifestyle Considerations and Concomitant Therapy sections of the protocol.

8.2. Efficacy Assessments

Efficacy parameters are not evaluated in this study.

8.3. Safety Assessments

Planned time points for all safety assessments are provided in the SoA. Unscheduled safety measurements may be obtained at any time during the study to assess any perceived safety issues.

8.3.1. Physical Examinations

A complete physical examination will include, at a minimum, head, ears, eyes, nose, mouth, skin, heart and lung examinations, lymph nodes, and gastrointestinal, musculoskeletal, and neurological systems.

A brief physical examination will include, at a minimum, assessments of general appearance, the respiratory and cardiovascular systems, and participant-reported symptoms.

Physical examinations may be conducted by a physician, trained physician's assistant, or nurse practitioner as acceptable according to local regulation.

Height and weight will also be measured and recorded as per the SoA. For measuring weight, a scale with appropriate range and resolution is used and must be placed on a stable, flat surface. Participants must remove shoes, bulky layers of clothing, and jackets so that only light clothing remains. They must also remove the contents of their pockets and remain still during measurement of weight.

Physical examination findings collected during the study will be considered source record and will not be required to be reported, unless otherwise noted. Any untoward physical examination findings that are identified during the active collection period and meet the definition of an AE or SAE (Appendix 3) must be reported according to the processes in Sections 8.4.1 to 8.4.3.

8.3.2. Vital Signs

8.3.2.1. Blood Pressure and Pulse Rate

Supine BP will be measured with the participant's arm supported at the level of the heart, and recorded to the nearest mm Hg after approximately 5 minutes of rest. The same arm (preferably the dominant arm) will be used throughout the study. Participants should be instructed not to speak during measurements. When triplicate measurements of supine BP or pulse rate are required per SoA, measurements should be collected 2-4 minutes apart.

The same properly sized and calibrated BP cuff will be used to measure BP each time. The use of an automated device for measuring BP and pulse rate is acceptable; however, when done manually, pulse rate will be measured in the brachial/radial artery for at least 30 seconds. When the timing of these measurements coincides with a blood collection, BP and pulse rate should be obtained prior to the nominal time of the blood collection.

Additional collection times, or changes to collection times, of BP and pulse rate will be permitted, as necessary, to ensure appropriate collection of safety data.

Any untoward vital sign findings that are identified during the active collection period and meet the definition of an AE or SAE (Appendix 3) must be reported according to the processes in Sections 8.4.1 to 8.4.3.

8.3.2.2. Respiratory Rate

Respiratory rate will be measured after approximately 5 minutes of rest in a supine position by observing and counting the respirations of the participant for 30 seconds and multiplying by 2. When BP is to be taken at the same time, respiration measurement will be done during the 5 minutes of rest and before BP measurement.

8.3.2.3. Body Temperature

Body temperature will be measured orally. No eating, drinking, or smoking is allowed for 15 minutes prior to the measurement.

8.3.3. Electrocardiograms

Standard 12-lead ECGs will be collected at times specified in the SoA section of this protocol using an ECG system that automatically calculates the HR and measures PR, QT, QTcF, and QRS intervals. All scheduled ECGs should be performed after the participant has rested quietly for at least 5 minutes in a supine position.

Triplicate 12-lead ECGs will be obtained approximately 2 to 4 minutes apart; the average of the triplicate ECG measurements collected at -1.0, -0.5, and 0 hours pre-dose on Day 1 of each period will serve as each participant's baseline QTcF value.

To ensure safety of the participants, a qualified individual at the investigator site will make comparisons to baseline measurements. Additional ECG monitoring will occur if a) the mean value from the triplicate measurements for any postdose QTcF interval is increased by ≥60 ms from the baseline and is >450 ms; or b) an absolute QT value is ≥500 ms for any scheduled ECG. If either of these conditions occurs, then a single ECG measurement must be repeated at least hourly until QTcF values from 2 successive ECGs fall below the threshold value that triggered the repeat measurement.

For single ECG collection, additional ECG monitoring will occur if a) a postdose QTcF interval is increased by ≥60 ms from the baseline **and** is >450 ms; or b) an absolute QT value is ≥500 ms for any scheduled ECG. If either of these conditions occurs, then 2 additional ECGs will be collected approximately 2 to 4 minutes apart to confirm the original measurement. If the QTcF values from these repeated ECGs remain above the threshold value, then a single ECG must be repeated at least hourly until QTc values from 2 successive ECGs fall below the threshold value that triggered the repeat measurement.

If a) a postdose QTcF interval remains ≥ 60 ms from the baseline and is ≥ 450 ms; or b) an absolute QT value is ≥ 500 ms for any scheduled ECG for greater than 4 hours (or sooner, at the discretion of the investigator); or c) QTcF value get progressively longer, the participant should undergo continuous ECG monitoring. A cardiologist should be consulted if QTcF values do not return to less than the criteria listed above after 8 hours of monitoring (or sooner, at the discretion of the investigator).

In some cases, it may be appropriate to repeat abnormal ECGs to rule out improper lead placement as contributing to the ECG abnormality. It is important that leads be placed in the

same positions each time in order to achieve precise ECG recordings. If a machine-read QTc value is prolonged, as defined above, repeat measurements may not be necessary if a qualified medical provider's interpretation determines that the QTcF values are in the acceptable range.

ECG values of potential clinical concern are listed in Appendix 8.

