- 8. Renal impairment as defined by an eGFR of <75 mL/min/1.73 m². Based upon participant age at screening, eGFR is calculated using the recommended CKD-EPI equations in Section 10.7.2 to determine eligibility (Screat-based formula) and to provide a baseline (Screat-Scys combined formula) to quantify subsequent kidney safety events. For eligibility assessment based upon estimated renal function, the higher of the screening and baseline eGFR values may be used.
- 9. Standard 12-lead ECG at Screening that demonstrates clinically relevant abnormalities that may affect participant safety or interpretation of study results (eg, QTcF >450 ms, complete LBBB, signs of an acute or indeterminate age myocardial infarction, ST-T interval changes suggestive of myocardial ischemia, second- or third- degree AV block, or serious bradyarrhythmias or tachyarrhythmias). If QTcF exceeds 450 ms, or QRS exceeds 120 ms, the ECG should be repeated twice and the average of the 3 QTcF or QRS values used to determine the participant's eligibility. Computer-interpreted ECGs should be overread by a physician experienced in reading ECGs before excluding a participant.
- 10. Participants with ANY of the following abnormalities in clinical laboratory tests at screening, as assessed by the study-specific laboratory and confirmed by a single repeat test, if deemed necessary:
 - ALT, AST, or bilirubin ≥1.05 × ULN. Participants with an elevated total bilirubin consistent with Gilbert's Disease may have a direct bilirubin measured and would be eligible for this study provided the direct bilirubin level is ≤ ULN;
 - TSH > ULN
 - HbA1c ≥6.5%;

- Hematuria as defined by $\geq 1+$ heme on urine dipstick;
- Albuminuria as defined by urine albumin/creatinine ratio (UACR) >30 mg/g.

Other Exclusion Criteria:

- 11. History of alcohol abuse or binge drinking and/or any other illicit drug use or dependence within 6 months of Screening. Binge drinking is defined as a pattern of 5 (male) and 4 (female) or more alcoholic drinks in about 2 hours. As a general rule, alcohol intake should not exceed 14 units per week (1 unit = 8 ounces (240 mL) beer, 1 ounce (30 mL) of 40% spirit, or 3 ounces (90 mL) of wine).
- 12. Use of tobacco/nicotine containing products in excess of the equivalent of 5 cigarettes/day or 2 chews of tobacco/day.

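### Protocol 8.3.3 puts the absolute trigger for extra ECGs on uncorrected QT, so a QTcF just above the 500 ms withdrawal value can go untriggered; the SAP omits the promised QT >500 ms tabulation

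*Protocol*

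**What the plan says.** **Triggers (protocol 8.3.3).** For triplicate ECGs, additional monitoring starts in either of two cases:

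- (a) "the mean value from the triplicate measurements for any postdose QTcF interval is increased by ≥60 ms from the baseline", and that mean is also above 450 ms; or
- (b) "an absolute QT value is ≥500 ms for any scheduled ECG".

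Criterion (b) is on uncorrected QT again in the single-ECG paragraph and in the paragraph on moving to continuous monitoring.

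**What follows a trigger (protocol 8.3.3).** These steps are judged on corrected QT:

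- Repeats and release: "a single ECG measurement must be repeated at least hourly until QTcF values from 2 successive ECGs fall below the threshold value".
- Confirmation of a single ECG: "If the QTcF values from these repeated ECGs remain above the threshold value", hourly repeats follow.
- Referral: "A cardiologist should be consulted if QTcF values do not return to less than the criteria listed above after 8 hours of monitoring".

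**Withdrawal (protocol 7.1.3).** "A participant who meets either bulleted criterion based on the average of triplicate ECG readings will be withdrawn from the study intervention". The two criteria are QTcF above 500 ms, or a QTcF rise above 60 ms with QTcF above 450 ms.

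**Entry limit (protocol 5.2, criterion 9).** The 450 ms QTcF limit belongs to a "Standard 12-lead ECG at Screening that demonstrates clinically relevant abnormalities". Baseline is then taken afresh on Day 1 of each period, with no stated ceiling.

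**Reporting.** Protocol 9.3.1.1 commits to tabulating how often uncorrected QT exceeds 500 ms. SAP 6.1.5 and Appendix 2 give categories for QTcF, PR and QRS, and the listing of values above 500 msec is for QTcF only. SAP 2.1 declares no departure from the protocol's analysis plan.

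**The concern.** No trigger in 8.3.3 is an absolute QTcF of 500 ms, although that is the value at which 7.1.3 withdraws a participant. At heart rates above 60 bpm, QT is shorter than QTcF, so a QT trigger of 500 ms is the less sensitive of the two. Protocol 2.3.1 lists increased heart rate as a potential risk of this drug, which is the direction that weakens the trigger.

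What could be lost is the mandatory hourly ECG follow-up after a dose already taken. Withdrawal stops later dosing but does not itself order repeat ECGs.

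The reporting gap does not depend on how 8.3.3 is read. The protocol promises a specific tabulation within the primary safety endpoint, and no SAP output delivers it.

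**Working it through.** The plan states no figure to reproduce. The check asks which QTcF values above 500 ms meet neither (a) nor (b).

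**Inputs.** The triggers are from protocol 8.3.3 and the withdrawal value from 7.1.3. SAP 3.1.5 gives the Fridericia formula, QTcF = QT/(RR)^(1/3) with RR = 60/HR, so QT = QTcF × (60/HR)^(1/3). Participants' heart rates are assumed. Protocol 2.3.1 gives only rises for a marketed drug of the class: a mean of 2 to 3 bpm, with 10 to 20 bpm in some people.

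**Step 1: where (a) leaves a gap.** Criterion (a) is first met at baseline + 60 ms.

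| Period baseline QTcF (ms) | (a) first met at (ms) | QTcF above 500 not caught by (a) |
|---|---|---|
| 440 or less | 500 or less | none |
| 441 | 501 | above 500, below 501 |
| 445 | 505 | above 500, below 505 |
| 447 | 507 | above 500, below 507 |
| 450 | 510 | above 500, below 510 |
| 460 | 520 | above 500, below 520 |

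The last row is possible because the 450 ms limit is applied only at screening.

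**Step 2: when (b) also misses.** QT is below 500 ms when HR > 60 × (QTcF/500)^3:

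- QTcF 501: above 60.4 bpm
- QTcF 505: above 61.8 bpm
- QTcF 510: above 63.7 bpm

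**Step 3: example.** Take a baseline of 447, a post-dose triplicate-mean QTcF of 505 and 70 bpm.

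- The rise is 505 − 447 = 58 ms, so (a) is not met.
- QT = 505 × (60/70)^(1/3) = 479.7 ms, so (b) is not met.
- QTcF is above 500 ms, so 7.1.3 withdrawal is met.

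**Step 4: what the schedule provides without a trigger.** Tables 1 and 2 of the protocol place post-dose ECGs at 0.5, 1, 2, 3, 4, 6, 8, 10, 24, 36, 48 and 72 h. Up to 10 h they are at most 2 h apart. After that the intervals are 14, 12, 12 and 24 h. A value first seen at 10 h is next checked on schedule at 24 h, and Day 1 telemetry is scheduled only to 8 h.

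**Step 5: the SAP.** QT is summarized by treatment and timepoint. Unplanned ECGs are listed and enter only the categorical summaries, and those have no QT category. The frequency of QT values above 500 ms therefore appears in no specified output.

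**The case against.** **QT is probably a slip.** The release rule is on QTcF, and a later sentence reads "If a machine-read QTc value is prolonged, as defined above, repeat measurements may not be necessary", as if the triggers had all been on corrected QT. This is plausible. But 8.3.3 also names QT and QTcF as separate measurements and uses QT in criterion (b) three times, so a site may apply it literally. If it is a slip, the correction is still needed.

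**Other safeguards cover the gap.** This largely stands:

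- Withdrawal under 7.1.3 does not depend on the 8.3.3 triggers.
- 8.3.3 has a criterion (c): progressively longer QTcF leads to continuous monitoring. A climb from 447 to 505 ms could well meet it, although no number is attached.
- Appendix 8 lists QTcF above 500 ms as a possible SAE.
- The investigator can order ECGs at any time.

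None of these is a fixed hourly requirement, but together they make the consequence small.

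**Criterion (b) can be read per tracing.** It mentions no averaging. With QTcF 505 at 63 bpm, QT is 505 × (60/63)^(1/3) = 496.9 ms. If tracings vary independently with an SD of 3 to 8 ms (an assumption; the documents give none), the chance that at least one of three reaches 500 is 1 − [Φ(3.1/SD)]^3, about 39% to 72%. So the gap is weak near 60 to 64 bpm. At 70 bpm the shortfall is 20.3 ms and the same formula gives at most about 2%.

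**Unseen sponsor standards may produce the QT table.** They may, but the SAP does not say so.

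**Conclusion.** Both parts hold, at minor severity.

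**Trigger.** On a literal reading, the absolute trigger can miss a QTcF above the withdrawal value. This needs a period baseline above 440 ms and a heart rate clearly above about 60 to 64 bpm. The uncovered range is under 10 ms for period baselines up to 450 ms, and wider if a period baseline is higher. The heart rates are assumed, and no probability is claimed.

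**Tabulation.** One promised output is unspecified. It can be recovered from data already collected.

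A reader might infer more than the documents support:

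- *That a participant with QTcF above 500 ms could go on being dosed.* No. 7.1.3 withdraws on QTcF regardless of the triggers.
- *That releasing a QT-triggered participant on QTcF at a slow heart rate is a harm.* Not shown. At 45 bpm, a QT of 500 ms is a QTcF of 454.3 ms, so 7.1.3's absolute value is far off. If the QTcF rise also meets (a), that trigger is followed on its own measure.
- *That the protocol promises a number of participants with QT above 500 ms.* It promises the frequency of such values. The number and percentage of participants are specified for the QTcF categories.

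**What to change.** **Protocol 8.3.3.** In the triplicate, single-ECG and continuous-monitoring paragraphs, set criterion (b) to an absolute QTcF of 500 ms or more. If the QT criterion was intended, keep QT of 500 ms or more as an additional trigger. State that each trigger is confirmed and released on its own measure. Every QTcF above 500 ms then meets a trigger, whatever the baseline or heart rate. Section 7.1.3 and Appendix 8 need no change.

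**SAP 6.1.5 and Appendix 2.** Add one row giving the frequency of uncorrected QT values above 500 msec by treatment, counting planned and unplanned post-dose ECGs as for QTcF. A maximum post-dose QT endpoint in 3.1.5 is optional and not needed to meet the promise. SAP 2.1 can then stay as it is.

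**Cost.** A short protocol amendment with IRB/EC approval before use, possibly a few more repeat ECGs, and one table row from data already collected.
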